14.0 Risks to Subjects

14.1 List the reasonably foreseeable risks, discomforts, hazards, or inconveniences to the subjects related the subjects' participation in the research. Include as may be useful for the IRB's consideration, a description of the probability, magnitude, duration, and reversibility of the risks. Consider physical, psychological, social, legal, and economic risks.

Response: The risks involved in inclusion in the study include the risk of additional exposure to radiation from the investigational CBCT scan. The investigational cone beam CT scanner exposes the patient to approximately 50% less radiation per scan than a conventional CT scanner, the total dose delivered to study subjects will be half that of a single conventional CT scan. (Carrino et al 2014) The investigational scanner will be shielded per manufacturer specifications (see **Attachment B**). The subject will be shielded from radiation to the thyroid and genitals with commercially available shields. To address the risk of pain caused by the need for weight bearing and/or flexion of an injured knee, the scan will only last about 25 seconds. The subject will be provided with assistance entering and exiting the scanner, and the handles attached to the housing of the scanner can be held by the subject for balance (but not for substantial unloading of weight bearing) on the extremity to prevent falling.

14.2 If applicable, indicate which procedures may have risks to the subjects that are currently unforeseeable.

Response: There are no unforeseeable risks to report.

14.3 If applicable, indicate which procedures may have risks to an embryo or fetus should the subject be or become pregnant.

Response: The CBCT scan does involve a low dose of radiation, thus women who are currently pregnant will not be included in the study.

14.4 If applicable, describe risks to others who are not subjects.

PROTOCOL TITLE: Comparison of a novel weight bearing cone beam computed tomography (CT) scan to gravity stress X-ray for determining instability of supination-external rotation type ankle fractures

Response: Technicians who are running the CBCT scanner will be properly trained in safety and take the necessary precautions to protect themselves from radiation exposure. There are no risks to family or those in close contact with the subject during their participation in the trial (see **Attachment B**).

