Study Visit: The subject will undergo a weight bearing CBCT scan of their affected ankle with the investigational portable cone beam CT scanner. This will be done at the same time or within 7 days as the gravity stress X-ray that is part of the routine clinical work-up for this injury. The scan with the investigational CBCT scanner is estimated to last approximately 25 seconds. The patient will be weight-bearing during the scan and can hold on to the built-in handles of the scanner for stability during the scan. The subject will be shielded from radiation to the thyroid and genitals with commercially available shields. The risks involved with this study include the risk of additional exposure to radiation delivered by the investigational CT scan. The investigational CBCT scanner exposes the patient to approximately 50% less radiation per scan than a conventional CT scanner. (Carrino et al 2014) With the investigational CBCT scan, there is the risk of pain caused by the need for weight bearing and/or flexion of an injured ankle. If for any reason the subject experiences undue discomfort the study will be stopped and the patient will be excluded from the study if the scan cannot be performed.

The patient will also fill out a visual analogue pain scale after both the investigational CT scan and gravity stress X-ray (**Attachment D**).

Reference: Carrino, J.A., et al., Dedicated cone-beam CT system for extremity imaging. *Radiology*, 2014. 270(3): p. 816-824.

9.3 Describe procedures performed to lessen the probability or magnitude of risks.

Response: The risks involved in inclusion in the study include the risk of additional exposure to radiation from the investigational CT scan. The investigational cone beam CT scanner exposes the patient to approximately 50% less radiation per scan than a conventional CT scanner. (Carrino et al 2014) The investigational scanner will be shielded per manufacturer specifications (see attachment B). The subject will be

PROTOCOL TITLE: Comparison of a novel weight bearing cone beam computed tomography (CT) scan to gravity stress X-ray for determining instability of supination-external rotation type ankle fractures

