Risk to Human Subjects: The main risk to the subjects of study is due the use of ionizing radiation during the imaging procedure. The estimated dosage that will be received by the study participants is ~ 0.14 mSv. This dose is comparable to or less than the typical dose delivered during a conventional diagnostic CT scan – 0.16 mSv as reported by Biswas et al. (Radiation exposure from musculoskeletal computerized tomographic scans. JBJS A (91): 1882-1889, 2009) Radiation dose at less than 1 mSv is orders of magnitude less than that associated with possible long term health risks, even by the most conservative estimates. (Brenner and Hall. Computed tomography – an increasing source of radiation exposure. NEJM 375(22): 2277, 2007) This statement is also consistent with position statement of the American Association of Physicists in Medicine(AAPM), which states: “risks of medical imaging at effective doses below 50 mSv for single procedures or 100 mSv for multiple procedures over short periods are too low to be detectable and may be nonexistent.”

The prototype of the scanner to be used in this study was previously reported by Carrino et al (Dedicated cone-beam CT system for extremity imaging. Radiology 270(3): 816-824, 2014) to deliver absolute dose of 9.0 mGy, compared to 39.7 mGy for the same scan on a conventional CT scanner. As further outlined by Biswas; these levels of radiation dose are approximately equal to the dose of two PA chest radiographs, or two transatlantic flights on a commercial airplane, and are “essentially negligible/trivial...” within the context of patient risk associated with radiation exposure. In most patients, it would be expected that the diagnostic information yielded by the CT scan would supersede any concern about excessive radiation exposure.

It is therefore contended that the dose levels associated with the proposed protocol will present negligible risk to the health, safety, or welfare of the study participants.

Risk Determination: Guidance for determination of significant(SR) or non-significant risk(NSR) risk can be found in part 812.3(m) of the CFR Title 21 and in the FDA document *Information sheet guidance for IRBs, clinical investigators, and sponsors*.

The FDA definition of a significant risk device is that the device:

- Is intended as an implant and presents a potential for serious risk to the health, safety, or welfare of a subject;
Assessment: The scanner is **not** intended as an implant

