- Is purported or represented to be for use supporting or sustaining human life and presents a potential for serious risk to the health, safety, or welfare of a subject;
Assessment: The scanner is **not** for use in supporting or sustaining human life...
- Is for a use of substantial importance in diagnosing, curing, mitigating, or treating disease, or otherwise preventing impairment of human health and presents a potential for serious risk to the health, safety, or welfare of a subject;
Assessment: In this study, the scanner is **not** for use in diagnosing, curing, mitigating, or treating disease. Enrolled subjects will undergo the normal physician encounter and diagnostic testing associated with their clinical condition. The imaging

PROTOCOL TITLE: Comparison of a novel weight bearing cone beam computed tomography (CT) scan to gravity stress X-ray for determining instability of supination-external rotation type ankle fractures

procedure for this study will be taken in addition to the normal diagnostic testing (conventional CT scan). The scan results will not influence patient treatment or clinical management decisions before the diagnosis is established by the medically established standards of history, physical examination, and imaging studies.

- Otherwise presents a potential for serious risk to the health, safety, or welfare of a subject.

Assessment: With regard to the use of ionizing radiation, the primary potential risk to be considered is the induction of cancer, which is a function of many factors – most notably the level of radiation dose and the age of the patient at the time of exposure. The study only includes subjects 16 years or older. As noted above, the radiation dose associated with the scanner is ~0.14 mSv, which is comparable to or less than that of conventional diagnostic CT of the extremities. As noted by Biswas; these levels of radiation dose are “essentially negligible/trivial...” within the context of patient risk associated with radiation exposure. Radiation dose at less than ~1 mSv is orders of magnitude lower than the dose believed to be associated with health risk, even by the most conservative of estimates. Together, these factors suggest an insignificant risk to study participants associated with radiation exposure.

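### Does the risk section's claim of half the conventional CT dose, which Attachment C's figures do not reproduce, require a change to the plan?

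*Combined protocol and SAP*

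**What the plan says.** The protocol compares the cone-beam scanner's dose with conventional CT in two places.

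- **Procedures and risk text.** Sections 9.2 and 9.3 say the investigational scanner gives "approximately 50% less radiation per scan than a conventional CT scanner". Section 14.1 repeats this and adds that "the total dose delivered to study subjects will be half that of a single conventional CT scan". All three cite the 2014 report on a dedicated cone-beam system for extremities.
- **Attachment C (non-significant-risk statement).** It cites the same 2014 report with the same title, journal, volume and pages. It opens with "The prototype of the scanner to be used in this study was previously reported" and says the prototype was found to "deliver absolute dose of 9.0 mGy, compared to 39.7 mGy for the same scan on a conventional CT scanner".

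Attachment C also gives an absolute estimate for this study: "The estimated dosage that will be received by the study participants is ~ 0.14 mSv". It sets this beside a typical 0.16 mSv taken from a different cited study, and describes the relation only in words: "This dose is comparable to or less than the typical dose delivered during a conventional diagnostic CT scan". The risk determination later in the attachment repeats the estimate and the description: "the radiation dose associated with the scanner is ~0.14 mSv, which is comparable to or less than that of conventional diagnostic CT".

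Sections 7.1 and 9.2 describe one cone-beam scan per subject, in addition to the routine gravity stress X-ray.

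**The concern.** One cited report appears to support two different comparisons: about half the conventional dose in the risk text, and under a quarter in Attachment C. A reader who then reaches the mSv figures finds a third description, in which the study dose is merely no higher than conventional CT.

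Section 14.1 is where the ethics board is asked to weigh the size of the risks. Attachment C says of this one, "The main risk to the subjects of study is due the use of ionizing radiation during the imaging procedure", and section 15.2 says subjects gain no direct benefit. If the relative dose in the risk section were wrong in the favourable direction, the board could be judging the study on an understated exposure. That would be a reason to act even though no statistical result depends on it.

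**Working it through.** **Inputs**

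| Quantity | Value | Where |
|---|---|---|
| Stated reduction per scan | about 50% | Sections 9.2, 9.3, 14.1 |
| Stated total relative to one conventional CT | one half | Section 14.1 |
| Cone-beam and conventional dose, same scan | 9.0 and 39.7 mGy | Attachment C, 2014 report |
| Estimated participant dose | about 0.14 mSv | Attachment C (twice) |
| Typical conventional CT dose | 0.16 mSv | Attachment C, a different study |
| Cone-beam scans per subject | 1 | Sections 7.1, 9.2 |

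**Step 1. Is section 14.1 consistent with itself?** With one scan, total ratio = 1 × (1 − 0.50) = 0.50. Yes: the per-scan and total statements agree.

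**Step 2. Does the pair credited to the same report give one half?**

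- Ratio = 9.0/39.7 = 0.227.
- Reduction = 1 − 0.227 = 0.773, about 77%.
- Allowing for rounding of the printed figures: 8.95/39.75 = 0.225 to 9.05/39.65 = 0.228.
- One half of 39.7 would be 19.85 mGy, which is 19.85/9.0 = 2.2 times the figure given.

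The answer is no. Neither rounding nor the word for approximation in the text stretches 50% to 77%.

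**Step 3. Do the mSv figures bear on the 50% statement?** Their ratio is 0.14/0.16 = 0.875. The documents never state this ratio. It combines an estimate for this study with a typical value from another study, in a different dose quantity from the mGy pair. In words, Attachment C allows the study dose to be comparable or lower, and one half is lower, so the wording does not contradict section 14.1. The ratio is indicative at best.

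**Step 4. Which way does any error run?**

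- Against the mGy pair, one half overstates the relative dose (0.50 against 0.227), which is the cautious direction.
- Against the mSv figures, one half of 0.16 would be 0.08 mSv, and the estimate is about 0.14 mSv. The difference is 0.14 − 0.08 = 0.06 mSv. Attachment C treats anything under about 1 mSv as orders of magnitude below the level linked to health risk, and 0.06/1 is 6% of that mark.

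**Step 5. What uses the relative figure?**

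- The non-significant-risk reasoning in Attachment C uses the absolute dose, about 0.14 mSv against 1 mSv, and not the 50%.
- Even as an illustration that carries the ratios over to the 0.16 mSv comparator, the implied doses would be 0.50 × 0.16 = 0.08 mSv and 0.227 × 0.16 = 0.036 mSv. Both are below the 0.14 mSv relied on, so the argument already rests on the least favourable of the three.
- Eligibility (section 3.1), the analysis plan (11.1) and the power calculation (11.2) do not mention dose.

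**The case for a change.** The strongest case for acting is that the comparison sits in the section written for the ethics board, concerns what the attachment itself names as the main risk, and can be shown wrong or unexplained from the documents alone. The direction of any error is also unsettled: one half is cautious beside the mGy pair but may be favourable beside the participant estimate. A wording correction costs almost nothing.

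Much of this stands. The mismatch between sections 9.2, 9.3 and 14.1 and the mGy pair is in the text. A change of scanner generation does not fully explain it, because both statements cite the same report. The passages should agree, in one named dose quantity with its source.

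Three things limit it.

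- The documents prove an unexplained difference, not a wrong figure. Neither statement names a body part or protocol, and one report may contain several comparisons. The mGy pair also belongs to an earlier prototype, while Attachment C describes the study device as third generation.
- The suggestion that one half understates exposure depends entirely on the mixed-source mSv ratio.
- The board has the absolute estimate, stated the same way twice, and that is the quantity from which harm is judged. Subjects do not receive the cone-beam scan in place of a conventional CT under section 9.2. They receive it beside a gravity stress X-ray, so the relative figure is only a yardstick.

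**Conclusion.** The concern is accurate as a reading of the text but does not call for a change to the plan. It is a clerical inconsistency: one half stated, 0.227 (about 77% less) from the figures credited to the same report. Making sections 9.2, 9.3, 14.1 and Attachment C agree is ordinary editing, and which statement is right cannot be decided from these documents.

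Nothing the trial does or can conclude depends on it. The risk classification rests on about 0.14 mSv, and the eligibility rules, the 20-subject sample size and the paired comparison of medial clear space are untouched.

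This conclusion assumes that one cone-beam scan is performed per subject, as sections 7.1 and 9.2 describe, and that the 0.14 mSv estimate applies to the device actually used. A materially different absolute dose would be a separate question, but the 50% statement is not evidence of one.

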15.0 Potential Benefits to Subjects

15.1 Describe the potential benefits that individual subjects may experience from taking part in the research. Include as may be useful for the IRB's consideration, the probability, magnitude, and duration of the potential benefits.

Response: There may be no potential benefits to subjects who enroll in the study.

15.2 Indicate if there is no direct benefit. Do not include benefits to society or others.

Response: There are no direct benefits to subjects who enroll in the study.

16.0 Vulnerable Populations

16.1 If the research involves individuals who are vulnerable to coercion or undue influence, describe additional safeguards included to protect their rights and welfare.

- *If the research involves pregnant women, review "CHECKLIST: Pregnant Women (HRP-412)" to ensure that you have provided sufficient information.*
- *If the research involves neonates of uncertain viability or non-viable neonates, review "CHECKLIST: Neonates (HRP-413)" or "HRP-414 – CHECKLIST: Neonates of Uncertain Viability (HRP-414)" to ensure that you have provided sufficient information.*
- *If the research involves prisoners, review "CHECKLIST: Prisoners (HRP-415)" to ensure that you have provided sufficient information.*
- *If the research involves persons who have not attained the legal age for consent to treatments or procedures involved in the research ("children"), review the "CHECKLIST: Children (HRP-416)" to ensure that you have provided sufficient information.*
- *If the research involves cognitively impaired adults, review "CHECKLIST: Cognitively Impaired Adults (HRP-417)" to ensure that you have provided sufficient information.*
- *Consider if other specifically targeted populations such as students, employees of a specific firm or*

PROTOCOL TITLE: Comparison of a novel weight bearing cone beam computed tomography (CT) scan to gravity stress X-ray for determining instability of supination-external rotation type ankle fractures

educationally/economically disadvantaged persons are vulnerable to coercion or undue influence. The checklists listed above for other populations should be used as a guide to ensure that you have provided sufficient information.

Response: This research does not involve any of these vulnerable populations.

17.0 Community-Based Participatory Research

17.1 Describe involvement of the community in the design and conduct of the research.

Response: NA, this is not a community-based study.

Note: “Community-based Participatory Research” is a collaborative approach to research that equitably involves all partners in the research process and recognizes the unique strengths that each brings. Community-based Participatory Research begins with a research topic of importance to the community, has the aim of combining knowledge with action and achieving social change to improve health outcomes and eliminate health disparities.

18.0 Sharing of Results with Subjects

18.1 Describe whether or not results (study results or individual subject results, such as results of investigational diagnostic tests, genetic tests, or incidental findings) will be shared with subjects or others (e.g., the subject’s primary care physicians) and if so, describe how it will be shared.

Response: The study results or individual subject results, such as results of investigational diagnostic imaging, will be shared with the study subjects if requested verbally or in writing. The study results may become public knowledge if included in a manuscript accepted for publication in peer reviewed scientific literature. Any and all identifying features of individual images will be de-identified before publication.

19.0 Setting

19.1 Describe the sites or locations where your research team will conduct the research.

Response: Research will be conducted at UBMD Orthopaedics & Sports Medicine. The investigational CBCT scanner will be located in the SkyView Room of the radiology department at ECMC.

19.2 Identify where your research team will identify and recruit potential subjects.

PROTOCOL TITLE: Comparison of a novel weight bearing cone beam computed tomography (CT) scan to gravity stress X-ray for determining instability of supination-external rotation type ankle fractures

Response: Subjects will be recruited & consented after undergoing an orthopaedic consultation at the ECMC Emergency Department or in the offices of the physicians of UBMD Orthopedics and Sports Medicine at ECMC or the Northtowns office ([name]).

19.3 Identify where research procedures will be performed.

Response: Subjects will be recruited & consented at ECMC Emergency Department or in the offices of the physicians of UBMD Orthopedics and Sports Medicine at ECMC or the Northtowns office ([name]). The investigational CBCT scan will be done in the SkyView room of the radiology department at ECMC.

19.4 Describe the composition and involvement of any community advisory board.

Response: NA, there will be no community advisory board involved in this study.

19.5 For research conducted outside of the organization and its affiliates describe:

- *Site-specific regulations or customs affecting the research for research outside the organization.*
- *Local scientific and ethical review structure outside the organization.*

Response: NA, research will not be conducted outside of the organization.

20.2 Justify the feasibility of recruiting the required number of suitable subjects within the agreed recruitment period. For example, how many potential subjects do you have access to? What percentage of those potential subjects do you need to recruit?

Response: In the past year, approximately 50-60 patients with potentially unstable SER type ankle fractures were treated by the study investigators. Based on our sample size calculation, we need to enroll 20 patients. Thus we should have a sufficient pool of subjects to recruit from.

20.3 Describe the time that you will devote to conducting and completing the research.

Response: We estimate that it will take about 8 months to 1 year to enroll all subjects, and about 6 months after that to complete the analysis and a manuscript.

20.4 Describe your facilities.

Response: Erie County Medical Center is a hospital with 550 licensed beds located in Buffalo, New York and is a member of the Great Lakes Health System. The hospital is affiliated with the University at Buffalo. The hospital is equipped with the latest information technology, including an electronic medical record system.

PROTOCOL TITLE: Comparison of a novel weight bearing cone beam computed tomography (CT) scan to gravity stress X-ray for determining instability of supination-external rotation type ankle fractures

20.5 *Describe the availability of medical or psychological resources that subjects might need as a result of anticipated consequences of the human research.*

Response: The radiology technician will periodically evaluate acquisition of the first CBCT scan to ensure maximum patient comfort and safety. Modifications will be made as appropriate and may include cushions, padding, external supports, or other changes when they add patient comfort or safety. Subjects will be withdrawn from the study if they cannot complete the investigational CBCT scan. Subjects can withdraw from the study at any time, for any reason. No other medical or psychological issues are expected to occur as a result of this study.

20.6 *Describe your process to ensure that all persons assisting with the research are adequately informed about the protocol, the research procedures, and their duties and functions.*

Response: Each of the persons assisting with the research has been involved in designing the study, and writing of this proposal. The investigative team will meet periodically to discuss the protocol, modify the research procedures as necessary, and review the results. All study personnel will be involved in preparing a manuscript based on the results of the study.

